8.3.11.2 Medication Error

For the purposes of this clinical study a medication error is an **unintended** failure or mistake in the treatment process for an IMP or AstraZeneca NIMP that either causes harm to the participant or has the potential to cause harm to the participant.

The full definition and examples of medication error can be found in Appendix B 4.

8.3.11.3 Drug Abuse

Drug abuse is the persistent or sporadic **intentional**, non-therapeutic excessive use of IMP or AstraZeneca NIMP for a perceived reward or desired non-therapeutic effect.

The full definition and examples of drug abuse can be found in Appendix B 4.

8.3.11.4 Drug Misuse

Drug misuse is the **intentional** and inappropriate use (by a study participant) of IMP or AstraZeneca NIMP for medicinal purposes outside of the authorised product information, or for unauthorised IMPs or AstraZeneca NIMPs, outside the intended use as specified in the protocol and includes deliberate administration of the product by the wrong route.

The full definition and examples of drug misuse can be found in Appendix B 4.

8.3.12 Medical Device Deficiencies

In this study any deficiency observed with a third-party medical device will be collected and reported to the manufacturer.

A medical device deficiency is an inadequacy of a medical device with respect to its identity, quality, durability, reliability, safety, or performance. Medical device deficiencies include malfunctions, use errors, and information supplied by the manufacturer.

8.4 Overdose

For guidance refer to AstraZeneca standard operating procedures Reporting of Individual Safety Events in Clinical Studies.

For this study, an overdose is defined as a participant receiving a dose of study intervention in excess of that specified in the IB, unless otherwise specified in this protocol.

- An overdose with associated AEs is recorded as the AE diagnosis/symptoms on the relevant AE modules in the eCRF and on the Overdose eCRF module.
- An overdose without associated symptoms is only reported on the Overdose eCRF module.

If an overdose on an AstraZeneca study intervention occurs in the course of the study, the Investigator or other site personnel inform appropriate AstraZeneca representatives immediately, but **no later than 24 hours** of when he or she becomes aware of it.

The designated AstraZeneca representative works with the Investigator to ensure that all relevant information is provided to the AstraZeneca Patient Safety data entry site **within one or 5 calendar days** for overdoses associated with an SAE (see section [8.3.9](#)) and **within 30 days** for all other overdoses.

8.5 Human Biological Samples

Instructions for the collection and handling of biological samples will be provided in the study specific Laboratory Manual. Samples should be stored in a secure storage space with adequate measures to protect confidentiality. For further details on Handling of Human Biological Samples see [Appendix C](#).

Samples will be stored for a maximum of 15 years from the date of the issue of the CSR in line with consent and local requirements, after which they will be destroyed/repatriated. The results from future analysis will not be reported in the CSR.

- Pharmacokinetic samples will be disposed of after the Bioanalytical Report finalisation or 6 months after issuance of the draft Bioanalytical Report (whichever is earlier), unless consented for future analyses.
 - Pharmacokinetic samples may be disposed of or anonymised by pooling. Additional analyses may be conducted on the anonymised, pooled, or individual PK samples to further evaluate and validate the analytical method. Any results from such analyses may be reported separately from the CSR.
- Remaining ADA sample aliquots will be retained at AstraZeneca or its designee for a maximum of 15 years following issue of the CSR. Additional use includes but is not limited to further characterisation of any ADAs, confirmation and/or requalification of the assay as well as additional assay development work. The results from future analysis will not be reported in the CSR.

8.5.1 Pharmacokinetics

- Blood samples will be collected for measurement of serum concentrations of AZD1402 as specified in the SoAs ([Table 1](#) and [Table 2](#)).
- Samples may be collected at additional timepoints during the study if warranted and agreed upon between the Investigator and the Sponsor, eg, for safety reasons. The timing of sampling may be altered during the course of the study based on newly available data (eg, to obtain data closer to the time of peak or trough matrix concentrations) to ensure appropriate monitoring.
- Serum samples will be used to analyse the PK of AZD1402. Samples collected for analyses of AZD1402 (serum) concentration may also be used to evaluate safety or efficacy aspects related to concerns arising during or after the study.
- Samples will be collected, labelled, stored, and shipped as detailed in the Laboratory Manual.

8.5.1.1 Part 1

Blood samples for PK assessments will be collected from all the participants at timepoints mentioned in the SoA ([Table 1](#)).

8.5.1.2 Part 2

A sparse PK sampling will be carried out for all participants in Part 2 of the study at timepoints mentioned in the SoA ([Table 2](#)).

Intense sampling will be performed for a subset of approximately 25% of participants in each treatment arm at timepoints mentioned in the SoA ([Table 2](#)). The participants in these subsets may be asked to stay in the clinic overnight for logistical reasons depending on the sampling timepoints.

8.5.1.3 Determination of Drug Concentration

Samples for determination of drug concentration in serum will be assayed by bioanalytical test sites operated by or on behalf of AstraZeneca, using an appropriately validated bioanalytical method. Full details of the analytical method used will be described in a separate Bioanalytical Report.

Placebo samples will not be analysed, unless there is a need to confirm that correct treatment has been given to study participants.

Drug concentration information that would unblind the study will not be reported to investigative sites or blinded personnel until the study has been unblinded.

Incurred sample reproducibility analysis, if any, will be performed alongside the bioanalysis of the test samples. The results from the evaluation, if performed, will be reported in a separate Bioanalytical Report.

8.5.2 Immunogenicity Assessments

Blood samples for determination of ADA in serum will be assayed by bioanalytical test site operated by or on behalf of AstraZeneca, using an appropriately validated bioanalytical method. A tiered testing scheme will be employed, with the first step being screening. Samples found positive in the screening step will be tested in the confirmatory step. Samples confirmed positive for ADA in the confirmatory step will undergo endpoint titre determination.

Remaining ADA aliquots will be banked and may be used for further characterisation of the ADA response. The results from these tests will be reported outside of the CSR and full details of the methods used will be described in a separate report. Blood samples for determination of ADA in serum will be collected as specified at timepoints mentioned in the SoAs ([Table 1](#) and [Table 2](#)).

Additional samples may be collected during the study if warranted and agreed upon between the Investigator and the Sponsor, eg, for safety reasons.

At the last Follow-up Visit in Part 1 only, if a participant's sample is confirmed ADA positive, the participant will be asked to return to provide another sample to evaluate whether or not ADAs persist.

Samples will be collected, labelled, stored, and shipped as detailed in the Laboratory Manual.

8.5.3 Pharmacodynamics

Collection of Samples

CCI

For storage, re-use and destruction of pharmacodynamic samples see Section 8.5 and Appendix C.

8.6 Human Biological Sample Biomarkers

8.6.1 Collection of Mandatory Samples for Biomarker Analysis

By consenting to participate in the study the participant consents to the mandatory research components of the study.

- Samples for biomarker research are required and will be collected from all participants in this study as specified in the SoAs.
- CCI [REDACTED]
- CCI [REDACTED]
- Blood samples for allergen-specific IgE will be collected for CCI [REDACTED] and tested in the case of AEs that have characteristics of a type I hypersensitivity-like response.

8.6.2 Collection of Optional Samples for Biomarker Analysis

Collection of optional samples for this part of biomarker analysis is part of this study as specified in the SoAs and is subject to agreement in the ICF addendum.

Blood samples will be collected from participants who have consented to participate in the part of biomarker component of the study. Participation is optional. Participants who do not wish to participate in the optional biomarker research may still participate in the study.

- CCI [REDACTED]
- CCI [REDACTED]

For storage, re-use and destruction of biomarker samples, see Section 8.5.

8.7 Optional Genomics Initiative Sample

Collection of optional samples for Genomics Initiative research is also part of this study as specified in the SoAs and is subject to agreement in the ICF addendum.

Blood sample for DNA isolation will be collected from participants who have consented to participate in the genetic analysis component of the study. Participation is optional. Participants who do not wish to participate in the genetic research may still participate in the study.

CCI

Details on processes for collection and shipment and destruction of these samples can be found either in the appendices or in the Laboratory Manual.

For storage and destruction of genetic samples see [Appendix D](#).

8.8 Health Economics

Not applicable.

9 STATISTICAL CONSIDERATIONS

9.1 Statistical Hypotheses

No statistical hypotheses will be tested for in Part 1 (Lead-in Cohort) of this study.

Part 2 (Main Cohort) of this study aims to demonstrate that AZD1402 improves FEV₁ compared to placebo.

The null hypotheses for the primary analysis in Part 2 (Main Cohort) are that there is no difference in the change from baseline at Week 4 in FEV₁ in AZD1402 treated participants compared to placebo-treated participants. The following comparisons will be performed:

- AZD1402 inhalation CCI mg CCI versus placebo inhalation CCI
- AZD1402 inhalation CCI mg CCI versus placebo inhalation CCI

No adjustments for multiple testing will be performed.

9.2 Sample Size Determination

In Part 1 (Lead-in Cohort), approximately 45 participants will be randomised. Part 1a will consist of 30 randomised participants and Part 1b will consist of 15 randomised participants. The sample size for Part 1 (Lead-in Cohort) is not based on any sample size calculation, but was chosen to obtain reasonable evidence of safety and tolerability without exposing undue number of participants to the study intervention. In Part 2 (Main Cohort), 73 evaluable participants per treatment arm will provide CCI% power using a 1-sided test and CCI% significance level to detect a difference of 175 mL in FEV₁ versus placebo. This is based on a

SD of **CCI** mL, derived from an inter-participant SD of **CCI** mL in change from baseline to Week 4, adjusted for 4 repeated measurements and a correlation of **CCI** between weekly measurements. Assuming a dropout rate of **CCI** %, approximately 80 evaluable participants per arm are needed. Due to the restricted recruitment into the **CC** mg dose arm the precision of inference in terms of statistical power will be less than **CCI** % for the comparisons **CC** mg versus placebo. A participant will be considered evaluable if he/she has baseline and Week 4 FEV₁ results available.

Part 2 will consist of approximately 165 participants.

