9.4.2.1 Primary Endpoint

The primary efficacy endpoint for Part 2 (Main Cohort) is the change from baseline in pre-bronchodilator FEV₁ at Week 4 compared to placebo.

The change from baseline in FEV₁ will be analysed using MMRM with treatment group, week (1 to 4), country, eosinophil count group (< 300, \geq 300 cells/ μ L), baseline FEV₁, and treatment-by-week interaction as fixed effects with participant as random effect. In this model, Week 1 to 4 corresponds to Visit 4 to 7. The within-participant correlation will be modelled using the unstructured covariance matrix. The Kenward-Roger approximation will be used to estimate the degrees of freedom.

Baseline for FEV₁ will be defined as the mean of the 2 measured values before first study intervention administration (30 minutes apart, at -45 minutes and -15 minutes, before study intervention) on Day 1.

Besides the main analysis in the FAS, treatment effect in primary endpoint will be evaluated in subgroups defined by measurements of eosinophil count (< 300 and \geq 300 cells/ μ L), and of FeNO (< 50 and \geq 50 ppb) evaluated at Day 1 pre-dose.

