4.10.1 Analysis and Data Conventions

No statistical hypotheses will be tested in Part 1 (Lead-in Cohort) of this study. Part 2 (Main cohort) of this study aims to demonstrate that AZD1402 improves FEV₁ compared to placebo.

The null hypotheses for the primary analysis in Part 2 is that there is no difference in the change from baseline at Week 4 (Visit 7) in pre-bronchodilator in-clinic FEV₁ in AZD1402 treated participants compared to placebo-treated participants.

The following comparisons will be performed:

- AZD1402 inhalation ^{CCI} mg ^{CCI} versus placebo inhalation ^{CCI}.
- AZD1402 inhalation ^{CCI} mg ^{CCI} versus placebo inhalation ^{CCI}

4.10.2 No formal comparisons between the different AZD1402 doses will be conducted. Adjustments for Covariates

The primary efficacy analysis for Part 2 will be adjusted for the following baseline covariates:

1. Country (stratification variable)
2. Baseline FEV₁

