4.11 Primary Efficacy Variable (Part 2)

The primary variable for the assessment of efficacy for Part 2 is the change from baseline pre-bronchodilator in-clinic FEV₁ at Week 4.

The change from baseline in pre-bronchodilator FEV₁ will be analysed using MMRM with treatment group, week (1 to 4), country, baseline FEV₁, and treatment-by-week interaction as fixed effects and with participant as random effect. In this model, Week 1 to Week 4 corresponds to Visit 4 to Visit 7.

The within participant correlation will be modelled using the unstructured covariance matrix. The Kenward-Roger approximation will be used to estimate the degrees of freedom. The REML method will be applied.

If the estimating algorithms will not converge, the following steps will be taken to simplify the model until convergence is achieved:

1. As a first step, try in order these 3 covariance structures: Toeplitz, the first-order autoregressive, and compound symmetry. Stop as soon as convergence is achieved.

Statistical Analysis Plan

2. If step 1 does not work, the treatment-by-week interaction will be removed from the last model in step 1, ie, from the model with compound symmetry.
3. In case non-convergence persists, the analysis will be changed to use the analysis of covariance (ANCOVA) instead of mixed-effects model for repeated measures.

Each treatment effect and treatment comparisons (all active treatments to placebo) will be estimated by the Least Square means (LS means) and the difference in LS means at the corresponding week (Week 1, Week 2, Week 3, Week 4) on the treatment-by-week interaction, along with their standard errors (SE) and 95% CIs, and the p-value corresponding to the between-treatment group difference. A plot showing the LS mean change (+/- SE) from baseline in FEV₁ over time within each treatment group will be provided.

Missing values will not be imputed. In this analysis it is thus assumed that any missing FEV₁ values are missing at random.

A listing of the primary efficacy data will be provided based on the FAS.

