4.19 Determination of Sample Size

In Part 1 (lead-in cohort), approximately 45 participants will be randomised. Part 1a will consist of 30 randomised participants and Part 1b will consist of 15 randomised participants. The sample size for Part 1 (lead-in cohort) is not based on any sample size calculation but was chosen to obtain reasonable evidence of safety and tolerability without exposing undue number of participants to the study intervention. In Part 2 (main cohort), 73 evaluable participants per treatment arm (████ mg and placebo) will provide █████% power using a 1-sided test and 5% significance level to detect a difference of 175 mL in FEV₁ between AZD1402 versus placebo. This is based on a SD of █████ mL, derived from an inter-participant SD of █████ mL in change from baseline to Week 4, adjusted for 4 repeated measurements and a correlation of █████ between weekly measurements. Assuming a dropout rate of

Statistical Analysis Plan

█████%, approximately 80 evaluable participants per arm are needed. Due to the restricted recruitment into the █████mg dose arm the precision of inference in terms of statistical power will be less than █████% for the comparisons █████mg versus placebo. A participant will be considered evaluable if he/she has a baseline and Week 4 FEV₁ results available. Part 2 will consist of approximately 165 participants.

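### The Part 2 power is calculated with a standard deviation adjusted for four repeated measurements, which suits the secondary four-week average and not the primary Week 4 comparison

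*Protocol*

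**What the plan says.** Protocol 9.2 plans 73 evaluable participants per arm to detect 175 mL in FEV₁. The power rests on an SD derived from the between-participant SD of "change from baseline to Week 4, adjusted for 4 repeated measurements and a correlation of" (value redacted). SAP 4.19 repeats this and shows the test level: "using a 1-sided test and 5% significance level to detect a difference of 175 mL".

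The definitions of the primary test point to Week 4:

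- Hypothesis, Protocol 9.1: "there is no difference in the change from baseline at Week 4 in FEV₁ in AZD1402 treated participants". SAP 4.10.1 has the same hypothesis and names Visit 7.
- Endpoint, Protocol 9.4.2.1: "The primary efficacy endpoint for Part 2 (Main Cohort) is the change from baseline in pre-bronchodilator FEV₁ at Week 4 compared to placebo".
- Evaluability, Protocol 9.2: "A participant will be considered evaluable if he/she has baseline and Week 4 FEV₁ results available".
- Estimator, SAP 4.11: "the difference in LS means at the corresponding week (Week 1, Week 2, Week 3, Week 4) on the treatment-by-week interaction", with "The within participant correlation will be modelled using the unstructured covariance matrix".

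The average over the four weeks is a separate secondary endpoint (SAP 3.2.1), estimated from the treatment factor (SAP 4.12.1).

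**The concern.** The calculation starts from the right quantity, the SD of the Week 4 change, and then replaces it with another. Averaging four equally variable, imperfectly correlated values gives a smaller SD, and that smaller SD describes the average. If it is used for a single-visit contrast, the power comes out too high.

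The stake is how a non-significant Week 4 result is read. If the stated power belongs to the average, a true 175 mL difference at Week 4 would be missed more often than the plan implies. An interim sample-size re-estimation (Protocol 9.5) would repeat the mismatch if it used the same adjusted SD.

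**Working it through.** **Inputs from the documents.** 73 evaluable per arm, 175 mL, one-sided 5% (SAP 4.19), equal arms of 80 randomised (Protocol 1.1). Power, both SDs, the correlation and the dropout rate are redacted. The 73 can therefore be neither reproduced nor refuted.

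**Assumptions.** Nominal power of 80% or 90%. Correlation ρ from 0.5 to 0.9. Adjustment equal to the variance of a mean of four equally correlated values, with factor f = (1 + 3ρ)/4. The documents do not state this formula. For a mean of changes, ρ should be the correlation between weekly changes, whereas the text speaks of weekly measurements.

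**Step 1: which contrast earns the factor.** Generalised least squares with complete data and 73 per arm gives these variances relative to 2/73:

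| ρ | Week 4, interaction model | Four-week average | Model without interaction (compound symmetry) |
|---|---|---|---|
| 0.5 | 1.000 | 0.625 | 0.625 |
| 0.7 | 1.000 | 0.775 | 0.775 |
| 0.8 | 1.000 | 0.850 | 0.850 |
| 0.9 | 1.000 | 0.925 | 0.925 |

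Weeks 1 to 3 do nothing for the Week 4 contrast. The factor f appears for the average, and for the model that drops the interaction. In SAP 4.11 that model is only the second non-convergence fallback.

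**Step 2: power at Week 4 without a covariate.** By the noncentral t distribution, the SD giving 80% power at 73 per arm is 423 mL, and for 90% it is 360 mL. Dividing by √f restores the Week 4 SD:

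| ρ | Week 4 SD, nominal 80% (mL) | Power | Week 4 SD, nominal 90% (mL) | Power |
|---|---|---|---|---|
| 0.5 | 535 | 63% | 455 | 75% |
| 0.7 | 481 | 71% | 408 | 82% |
| 0.8 | 459 | 74% | 390 | 85% |
| 0.9 | 440 | 77% | 374 | 88% |

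Equivalently, the Week 4 difference detectable with the quoted power is 175/√f = 221, 199, 190 or 182 mL. Given f, this does not depend on the redacted power or SD.

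**Step 3: the planned baseline covariate.** Suppose the starting SD is not baseline-adjusted, compound symmetry holds across baseline and Weeks 1 to 4, and ρ is the correlation between FEV₁ values. With FEV₁ variance σ², the change variance is 2σ²(1 − ρ) and the residual variance after adjustment is σ²(1 − ρ²), a ratio of (1 + ρ)/2. Multiplying the Week 4 variances of step 2 by 0.75, 0.85, 0.90 or 0.95 gives power of 73/77/78/79% (nominal 80%) or 85/87/88/89% (nominal 90%). The covariate removes (1 − ρ)/2 of the variance where the assumed adjustment removed 3(1 − ρ)/4, so it makes good two thirds of it.

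**Step 4: dropouts in the full analysis set.** With 80 randomised and 73 having Week 4 data, the other 7 can contribute through earlier visits. This adds about 0.5 to 3 points, depending on ρ and on when they leave. At nominal 80% without the covariate, power becomes 63% to 64% at ρ = 0.5 and 78% to 80% at ρ = 0.9.

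**The case against.** The strongest reply is that no arithmetic error is visible. The text says only that one SD is derived from another. The formula and even the direction of the adjustment are inferred, and every figure that could settle the matter is redacted. This stands as a limit on the size. It does not remove the mismatch, because the adjustment and the endpoint are both named in readable text and do not belong together.

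A second reply is that step 2 does not describe the planned analysis. The model uses all observed data in the full analysis set and adjusts for baseline FEV₁. This also stands: at high correlation the covariate and the recovery of dropouts bring the power close to nominal. Still, the documents give repeated measurements, not baseline adjustment, as the basis of the adjusted SD.

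A third reply is that Protocol 9.5 allows an increase from 80 to 107 per arm. Since 80/107 = 0.748, this would restore nominal power, without the covariate, if ρ is about 0.66 or more. It mitigates only in part, because the interim is optional and the text does not say which SD it would use.

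Finally, the practical consequence is modest. The SAP was updated for anticipated closure, and the final analysis does not use the planning SD.

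**Conclusion.** The sizing text and the primary test do not match. As described, the quoted power fits the four-week average and is not the power of the Week 4 comparison. This conclusion rests on the visible wording and on step 1.

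The size is open. Under the assumed factor and a nominal 80%, the overstatement runs from near zero (high correlation, baseline covariate, dropouts partly recovered) to about 17 points (ρ = 0.5, completers only, no covariate).

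A reader might infer that Part 2 is underpowered by a known amount, or that the SD was certainly reduced. The documents support neither, since the formula is not given and the values are redacted. Nor does the redaction count against the plan. A reader might also infer that the trial's result is compromised. It is not: the Week 4 estimate, confidence interval and p-value are unaffected. The point should be fixed, with medium confidence about its practical weight.

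**What to change.** In Protocol 1.1 and 9.2 and SAP 4.19, do one of the following:

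- Restate the power of the Week 4 comparison using the Week 4 SD without the repeated-measurement adjustment. If a residual SD after baseline adjustment is available, use it and say so.
- State that the quoted power refers to the four-week average, and give the Week 4 power beside it.

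Base any interim sample-size re-estimation under Protocol 9.5, with its ceiling of 107 per arm, on the Week 4 SD.

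A small wording correction goes with this. After the dropout allowance, the number needed per arm is a number randomised, not evaluable. Change the word in the sample-size text of Protocol 1.1, in Protocol 9.2 and in SAP 4.19, to agree with the Part 2 design description in Protocol 1.1.

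The cost is one recalculation and some rewording. No extra participants are needed, but the stated Week 4 power may become less favourable.
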